## ASSESSMENT SCHEDULE See Section 1.2 STATISTICAL CONSIDERATIONS Sample size determination: It is anticipated that approximately 72 patients (67 to 77 patients) will be enrolled in this study (Dose Escalation and Expansion Parts). Dose Escalation Part It is anticipated that approximately 30 to 40 DLT-evaluable patients will be entered in the Dose Escalation Part. The actual sample size will vary depending on DLTs observed and number of dose levels actually explored. Any patient who is not evaluable for DLT, ie, who discontinues the study treatment before the end of Cycle 1 for any reason other than DLT, or who did not receive treatment as planned, will be replaced. The first 3 patients treated during the Dose Escalation Part of TED15138 will be replaced. Another 3 patients will be enrolled in DL1 and the trial will proceed according to the 3+3 design. Expansion Part It is hypothesized that SAR440234 would induce a response rate of 40% and that the null hypothesis for ORR is 20%. Under these hypotheses and using a Simon 2-stage design (optimal), with a 1-sided 10% significance level and a power of 90%, it is planned to enroll 37 patients in the Expansion Part of the study. Eleven (11) responses out of 37 patients will be necessary to reject the null hypothesis (H0 response rate = 20%). An interim analysis of the ORR will be done after treatment of the first 17 patients through 2 cycles. If 3 or fewer responses (CR, CRi, or PR) are observed, the Expansion Part will be stopped due to futility. Analysis population: The DLT-evaluable population in the Dose Escalation Part will include all patients who have received at least 5 out of 6, weekly IV administrations of SAR440234 in DL1 and DL2, patients who have received at least 6 out of 7 IV administrations of SAR440234 in DL ≥3, and patients who discontinue the IMP before completion of Cycle 1 because of a DLT. The all-treated/safety population for both Dose Escalation and Expansion Parts of the study will include all patients who have given their informed consent and who have received at least 1 dose (even incomplete) of SAR440234. Response evaluable patients are defined as patients from the all-treated/safety population with at least 1 post-baseline evaluable disease assessment allowing status evaluation. The ADA (ie, anti-SAR440234 antibody) population will include all patients from the all-treated/safety population with at least 1 available ADA result after IMP administration. The pharmacokinetic population will include patients from the all-treated/safety population with at least 1 evaluable drug concentration after IMP administration (whatever the cycle and even if incomplete). Safety and dose escalation primary analysis: DLTs occurring during the DLT observation period will be analyzed in the DLT-evaluable population. Adverse events meeting DLT criteria occurring at any additional cycle will be assessed and analyzed in the all-treated/safety population. Pharmacokinetic parameters will be summarized with descriptive statistics. Dose proportionality and accumulation will also be assessed on relevant parameters in the pharmacokinetic population. The safety profile will be summarized for all the treated patients, as well as separately, in the Dose Escalation Part and Expansion Part.

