# 6.6 EXPANSION COHORT TO CONFIRM THE MTD

Approximately 37 patients will be treated at the RP2D of SAR440234 to collect safety, pharmacokinetic, pharmacodynamic, and preliminary efficacy data. Patients treated at the RP2D in the Dose Escalation Part (except B-ALL patients) together with the patients treated in the Expansion Part to a total of the first 17 patients treated at the RP2D (Stage 1 Phase 2), will be included in the efficacy analysis.

Additional or unexpected toxicities will also be explored using all the data gathered during the study course (not only at the RP2D). The occurrence of cumulative toxicity, and toxicities meeting the DLT criteria observed after the DLT observation period, if any, will also be assessed. The preliminary antitumoral activity (ie, tumor response) of the drug will be evaluated according to the IWG 2003 recommendations for AML (19) and the revised 2000 criteria for HR-MDS (34), and the 2016 NCCN Guidelines for ALL (Appendix D, Appendix F, and Appendix G).

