# Nonhematological abnormalities:

- Any Grade ≥3 nonhematological AE unless either caused by disease progression or obviously unrelated cause or caused by a laboratory abnormality without associated clinical consequences that resolves within 5 days.
- Any TEAE that, in the opinion of the Principal Investigator and Sponsor, is of potential clinical significance such that further dose escalation would expose patients to unacceptable risk.
- Grade 3 or Grade 4 CRS.
- Grade 2 CRS if it persists for >48 hours or is present <48 hours before the time when the next planned dose of SAR440234 is due.

**Other:** IMP-related adverse reaction leading to a delay or omission of more than 2 weeks between 2 planned administrations of SAR440234 due to failure to improve to baseline or Grade  $\leq 1$ .

At the end of each appropriate cycle (ie, end of Cycle 1), each patient must be assessed by the Investigator as to whether or not the patient experienced a DLT. This information must be recorded on the appropriate eCRFs, and an electronic DLT notification (either DLT or not) will be sent to the Sponsor, before a subsequent cycle may begin.

The reported potential DLTs will be reviewed by the study committee in order to determine their relationship to the IMP.

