# 13.4.4 Analyses of safety data

# 13.4.4.1 Dose-limiting toxicities

The DLTs observed during DLT observation period will be summarized by dose level, as well as AEs that meet the DLT criteria in subsequent cycles. Details will be provided (characteristics of DLTs) by patient.

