1.2 OBJECTIVE AND ENDPOINTS

Table 2 - Objectives and endpoints

Objectives	Endpoints

Primary
 
• Dose Escalation Part: To determine the maximum tolerated dose (MTD)/maximum administered dose (MAD) of SAR440234 administered as a single agent in patients with R/R AML, HR-MDS, or B-ALL, and determine the recommended phase 2 dose (RP2D) for the subsequent Expansion Part.• Expansion Part: To assess the activity of single agent SAR440234	
• Dose Escalation Part: Incidence of DLT observed during the first 42 days following the first administration of IMP in the first cycle of treatment.• Dose Escalation Part: Incidence of allergic reactions/hypersensitivity and CRS/acute infusion reactions.• Expansion Part: Preliminary anti-leukemia activity as defined by the IWG for MDS or AML: Overall response rate (ORR) including CR, CRI, and partial response, Duration of response, Event-free survival.

Objectives	Endpoints
	at the RP2D in patients with R/R AML, or HR-MDS.

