Analysis of all adverse events

The overview of TEAEs with the details below will be generated:

- Any TEAE
- Any grade ≥ 3 TEAE
- Any treatment emergent SAE
- Treatment related TEAEs (overall and for each individual drug)
- Treatment related TEAEs of Grade ≥ 3 (overall and for each individual drug)
- Serious treatment related TEAEs (overall and for each individual drug)
- Grade 5 TEAE (any TEAE with a fatal outcome during the treatment-emergent period)
- Any TEAE leading to permanent partial intervention discontinuation (for each individual drug)

- Any TEAE leading to permanent full intervention discontinuation

The AE summaries of [Table 5](#) will be generated with number (%) of participants experiencing at least one event. The analyses will be performed for all grades combined and for grades ≥ 3 .

Table 5 - Analyses of adverse events

Type of AE	MedDRA levels
All TEAE	Primary SOC, HLT and PT
TEAE related to IMP (overall and for each drug) as per Investigator's judgment	Primary SOC and PT
Treatment emergent SAE	Primary SOC and PT
Treatment emergent SAE related to IMP (overall and for each drug) as per Investigator's judgment	Primary SOC and PT
TEAE leading to permanent full intervention discontinuation	Primary SOC and PT
TEAE leading to permanent partial intervention discontinuation (for each individual drug)	Primary SOC and PT
TEAE leading to death (death as an outcome of the AE as reported by the Investigator in the AE page)	Primary SOC and PT
Pre-treatment AE	Primary SOC and PT
Post-treatment AE	Primary SOC and PT
TEAE leading to dose interruption	Primary SOC and PT
TEAE leading to dose modification (including dose reduction, dose omission and cycle delay, excluding dose interruption)	Primary SOC and PT

Analysis of deaths

Deaths will be analyzed through a listing with following information:

- Death date
- Study period
- Reason of death
- For AE with fatal outcome: PT, date of onset, relationship

Analysis of adverse events of special interest (AESIs) and other AEs of interest

Adverse events of special interest (AESIs) and other AEs of interest will be selected for analyses as indicated in [Table 6](#). Listings with PT and grade will be provided.

Table 6 - Selections for AESIs and other AEs of interest

AESIs and other AEs of interest	Selection
DLT during cycle 1	e-CRF specific DLT page
Pregnancy of a female participant as well as pregnancy occurring in a female partner of a male participant	e-CRF specific pregnancy page

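### The SAP omits the protocol's planned summary of adverse events meeting DLT criteria after Cycle 1, and does not declare the change

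*SAP*

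**What the plan says.** The protocol commits to a later-cycle DLT analysis in three places.

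- Clinical Trial Summary, under the safety and dose escalation primary analysis: "Adverse events meeting DLT criteria occurring at any additional cycle will be assessed and analyzed in the all-treated/safety population".
- Section 6.6, on the expansion cohort: "toxicities meeting the DLT criteria observed after the DLT observation period, if any, will also be assessed".
- Section 13.4.4.1: DLTs in the observation period are to be summarized by dose level, "as well as AEs that meet the DLT criteria in subsequent cycles", with details by patient.

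The SAP defines the primary endpoint in Table 2 as "Incidence of DLT observed during the first 42 days following the first administration of IMP in the first cycle of treatment". Its only DLT output is the first row of Table 6 in Section 4.7.2, "DLT during cycle 1", selected from the "e-CRF specific DLT page". For everything in that table, "Listings with PT and grade will be provided". Appendix 2, the place for changes to protocol-planned analyses, is marked as not applicable.

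On data capture, protocol Section 9.1.1 states: "At the end of each appropriate cycle (ie, end of Cycle 1), each patient must be assessed".

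**The concern.** The Table 6 row is right for the 42-day endpoint. The problem is that its companion, the later-cycle analysis, has no counterpart anywhere in the SAP, and a reader of the SAP alone would not know that one had been planned.

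The later-cycle output is the one place where the protocol applies its own definition of a dose-limiting event beyond the first 42 days. A secondary objective is to characterize safety including cumulative adverse drug reactions, and this output bears directly on it. Without it, the report can show which events occurred late, but not which of them would have counted as dose-limiting, or at which dose level.

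**Working it through.** No sample size or power figure is involved. The check is a comparison of text, in four steps.

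**1. Is the analysis elsewhere in the SAP?** DLTs appear in the endpoint table (first 42 days), the sample size section (replacement of patients not evaluable for DLT), the DLT-evaluable population (Cycle 1 dosing) and Table 6 (Cycle 1). None covers Cycle 2 or later. So there are three statements of the plan in the protocol and no corresponding output in the SAP.

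**2. Does early termination account for it?** SAP Sections 4.3, 4.4 and 4.9 invoke early termination for the primary efficacy endpoint, the secondary efficacy endpoint and the interim analysis. Section 4.3 keeps the primary safety endpoints and sends them to Section 4.7. No safety analysis is cancelled on that ground.

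**3. Could the Table 6 row pick up later events anyway?** The investigator's DLT assessment is tied to the end of Cycle 1, so the DLT page cannot be relied on for later events. If the page did hold some, the row label would exclude them.

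**4. Can the other SAP outputs rebuild it?** The criteria are those of protocol Section 6.2.1.

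| DLT criterion | What decides it | Nearest SAP output | What is lost |
|---|---|---|---|
| Nonhematological, Grade 3 or higher | Grade, cause, 5-day rule for laboratory-only findings | Grade ≥3 adverse event tables | Cycle; the exclusions |
| Grade 4 hematological | 14 days without recovery (7 for febrile neutropenia); baseline status for some | Worst-value laboratory grading; Table 5 rows for dose modification and discontinuation | Duration; within-patient link to baseline; cycle |
| CRS Grade 3 or 4 | Grade | Grade ≥3 tables; CRS listing | Little beyond the label |
| CRS Grade 2 | More than 48 hours, or proximity to next dose | CRS listing, duration in day categories | The 48-hour cut; timing against next dose |
| Other clinically significant event | Principal Investigator and sponsor judgement | None | The judgement |
| Related reaction without recovery | Two weeks | None with a duration rule | Duration |

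Two details support the table.

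- SAP Section 4.7.2 counts repeat occurrences once per treatment phase at the worst grade. Under Section 4.1 the on-treatment phase runs from first dose to 30 days after the last. A Cycle 2 recurrence can therefore sit behind the same event in Cycle 1.
- CRS duration is listed as 1 day, 2 to 3 days, or more than 3 days; the protocol's CRS analysis (Section 13.4.4.2) planned hours. The SAP does not say how days are counted. If it is end date minus start date plus one, an event touching two dates lasts under 48 hours, and one touching three dates lasts between 24 and 72 hours. The middle category then mixes events on both sides of 48 hours. More than 3 days would always exceed 48 hours.

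**The case against.** The strongest reply is that little is hidden. All safety analyses use the all-treated population over the whole treatment-emergent period, with no cycle limit. Table 5 covers all-grade, Grade ≥3, serious, related and fatal events, and those leading to discontinuation, interruption or dose modification. The CRS listing spans all infusions. A persistent Grade 4 cytopenia attributed to the drug would normally lead to a dose change or discontinuation under Section 6.5.4, and so reach Table 5. This stands, and it narrows the gap to the duration-, baseline- and cycle-dependent criteria.

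It is also fair to say that the criteria cannot be programmed outright. They involve disease progression, unrelated causes and clinical opinion, and Section 9.1.1 has the Study Committee review relationship to the drug. That bears on how to do the analysis, not on whether it was planned.

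Three stronger readings are tempting, and the documents do not support them.

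- A reader might infer that late dose-limiting events vanish from the analysis. They do not; they lose their classification.
- A reader might infer that dose decisions are distorted, since Section 6.3 asks for later toxicity to be considered. Those decisions rest with the investigators, sponsor and Study Committee from ongoing review (Sections 6.3 and 6.10). This SAP was written after early termination and does not drive escalation.
- A reader might measure the loss by exposure. With 2, 3 or 4 lead-in doses out of 6, 7 or 7 Cycle 1 infusions, 4, 4 or 3 remain at target dose. Six more in Cycle 2 put 6/10 = 60% or 6/9 = 67% after Cycle 1. The arithmetic is right, but it describes a hypothetical patient completing two full cycles and counts infusions, not missed events.

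**Conclusion.** The point holds: a protocol-planned safety analysis is missing from the SAP, and Appendix 2 is wrong to report no change. The omission should be corrected or declared. Its consequence is possible under-reporting of later-cycle tolerability by dose level in a descriptive report. No conclusion about the primary 42-day DLT endpoint is affected.

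Two limits apply. If few or no patients went beyond Cycle 1, the missing output would be short or empty. And the SAP cites the amended protocol of 11 July 2019, while the protocol reviewed is dated 29 August 2019. The August summary of changes lists nothing on this analysis, so the July text is assumed to match, but it was not available to check.

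**What to change.** Add to SAP Table 6 a row for adverse events meeting DLT criteria in Cycle 2 or later. Report n (%) and a patient listing, by dose level and cycle, in the all-treated population. The number of target doses received before onset would be a useful optional column.

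State how events are identified: flag candidates from the adverse event, CRS and laboratory data, then confirm them by sponsor medical review. Note in the output that the flow charts schedule no routine marrow aspirate after Cycle 2, so marrow hypocellularity is not systematically observed from then on.

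Before programming, reconcile the two forms of the two-week criterion. Section 6.2.1 refers to how long the reaction lasts; Section 9.1.1 refers to the resulting gap or omission between planned administrations. These can classify the same patient differently.

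If the analysis is dropped on purpose, say so in Appendix 2 with the reason.

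The cost is one table or listing from data already collected, plus medical review of the flagged events. Declaring the omission costs a sentence or two.

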To minimize the risk of severe CRS, an intra-patient dose escalation in Cycle 1 is proposed, as shown in Table 1. Lead-in doses include the first 2 doses in DL1 and DL2 (ie, Week 1 and Week 2 administered doses), the first 3 doses in DL3 to DL5, and the first 4 doses in DL6 to DL8. After the lead-in doses, each patient will receive a fixed dose until the end of treatment, unless the dose needs to be decreased for safety reasons. DL1 to DL8 will achieve a range of lead-in doses from and a range of final doses from During each cycle, pharmacokinetic and pharmacodynamic data will be collected that will be used, together with acute safety monitoring, in both the Dose Escalation and Expansion Parts.

Cycle 1 (doses in ng/kg) **Dose Level** Week 1 Week 2 Week 3 Week 4 Week 5 Week 6 Day 15 Day 29 Day 36 Day 1 Day 4 Day 8 Day 22 DL1 DL2 DL3 DL4 DL5 DL6 DL7

Table 1 - Intra-patient dose escalation: Cycle 1

DL=dose level

DL8

For subsequent cycles, patients will maintain the maximum weekly dose that they achieved in Cycle 1, as shown in Table 2.

Table 2 - Patient dosing after Cycle 1

			Cycle ≥2 (do	ses in ng/kg)		
Dose Level	Week 1	Week 2	Week 3	Week 4	Week 5	Week 6
DL1						
DL2						
DL3						
DL4						
DL5						
DL6						
DL7						
DL8						

DL=dose level

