# **Study continuation**

The duration of each cycle of treatment is 42 days, with weekly administration of IMP (except for Cycle 1 Week 1 in DL  $\geq$ 3 when 2 administrations will be given).

The criteria for retreatment of patients are described in Section 6.5.

The dose given in the second or subsequent cycles will be the last dose given in the previous cycle. If there is a  $\geq$ 10-day interval between administrations of SAR440234, the next infusion must start with the lead-in doses appropriate for the selected dose level.

Additional pharmacokinetic data, safety and disease response will be assessed as indicated in the flow charts (Section 1.2) and when clinically indicated.

A Study Committee including the main Investigators, Sponsor's clinical team, and ad hoc experts, when appropriate, will regularly review the safety data, and will make recommendations as appropriate. The Study Committee will also decide the RP2D, including the recommended lead-in dose and schedule, for the Expansion Part in R/R AML and HR-MDS patients.

Additional (optional) cohort(s) beyond DL8, or intermediate dose levels, may be evaluated; the decision to proceed with these optional cohort(s), however, will be discussed with the Study Committee and will be based on the available safety, exploratory, and pharmacokinetic data.

It is anticipated that the number of patients enrolled in the Dose Escalation Part will be 30 to 40.

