# Analysis of CRS

The following summaries will be provided:

- Number (%) of patients experiencing CRS (all grades and by grade).
- Number (%) of patients experiencing CRS by action taken with study treatment.
- Number (%) of patients with infusion of occurrence.
- Duration of CRS event (in hours).

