# 13.4.4.4 Clinical laboratory evaluations

For patients with multiple occurrences of the same laboratory variable during the on-treatment period, the maximum grade (worst) per patient will be used. Hematological and clinical biochemistry toxicities will be assessed from laboratory test parameters. Each test result will be graded by NCI-CTC (v4.03). The number of patients with abnormal laboratory tests at baseline will be presented by grade. The frequency of patients in each grade of lab tests during treatment will be summarized. When appropriate, the summary table will present the frequency of patients with any grade of abnormal laboratory tests and with Grade 3 to 4 of abnormal laboratory tests. For patients with Grade 3 to 4 abnormal laboratory tests, additional analyses will be conducted to describe time to onset and dose to onset.

Further analyses could be provided to explore the dose and time to onset of safety endpoints of interest.

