4 STATISTICAL ANALYSES

4.1 GENERAL CONSIDERATIONS

In general, continuous data will be summarized using the number of observations available, mean, standard deviation, median, minimum, and maximum. Categorical and ordinal data will be summarized using the count and percentage of participants.

The baseline value is defined as the last available value before the first administration of SAR440234. For participants enrolled but not treated, the baseline value is defined as the last available value before enrollment.

Unless otherwise specified, analyses will be performed by part, by dose level (if applicable) and overall (if applicable).

All efficacy analyses will be performed on the efficacy population. Objective response rate, as well as all other efficacy variables will be derived using the Investigator's assessment.

All safety analyses will be performed on the all-treated population.

Analysis period

The analysis period will be divided into 3 segments:

- The **pre-treatment period** is defined as the period from when the participants give informed consent up to first administration of IMP.
- The **on-treatment period** (ie, treatment-emergent (TE) period) is defined as the period from the first IMP administration to the last IMP administration + 30 days.
- The **post-treatment period** is defined as the period from the end of the on-treatment period, ie, 31 days after the last administration of IMP.

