4.7.1.2 SAR440234 exposure

The dose information will be assessed by the following:

- Cumulative dose for SAR440234 (ng/kg): the cumulative dose is the sum of all doses from cycle 1 day 1 up to treatment discontinuation
- Actual dose intensity (ng/kg/week) for SAR440234:
$$\text{ADI} = \text{Cumulative dose (ng/kg)} / \text{Overall duration of exposure in weeks}$$
- Planned dose intensity (ng/kg/week) for SAR440234:

$$\text{PDI} = \text{Total planned dose (ng/kg)} / \text{Overall duration of exposure in weeks}$$

The total planned dose for SAR440234 will be calculated by the sum of the theoretical planned dose (ie, the intended dose as per CRF) over the duration of treatment.

- The relative dose intensity (RDI, in %) for SAR440234 is defined as

$$\text{Relative Dose Intensity} = \left(\frac{\text{Actual Dose Intensity}}{\text{Planned Dose Intensity}} \right) \times 100$$

It is an indicator of the feasibility of the chosen schedule of administration.

A listing will be provided for cumulative dose, actual dose intensity and relative dose intensity.

Dose or cycle modifications

- Cycle delay: A cycle is deemed to have been delayed if start date of the current cycle – start date of previous cycle >42 days.
- Dose delay: A dose is deemed to have been delayed if the infusion is made >1 day later than the scheduled administration.
- Dose omission: A dose is considered to be omitted if the dose is not administered at the scheduled visit and 1 or more doses are given afterwards.
- Dose interruption: An infusion is considered to be interrupted if the administration is stopped before the infusion is completed, regardless of whether or not the infusion is restarted.
- Dose reduction: a dose is deemed to have been reduced if the dose taken by a patient is lower than 80% of the intended dose.
- Reason for dose reduction.

Dose information variables will be provided in a listing:

- Cycle/day of occurrence
- Dose reduction Y/N
- Dose omission Y/N
- Dose interruption Y/N
- Cycle delay Y/N

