Symptomatic overdose with IMP/NIMP	e-CRF specific tick box in overdose page
CRS	e-CRF specific category in AE page

Further analyses of Cytokine release syndrome (CRS) with a listing providing a more detailed description of CRS by patient:

- Action taken
- Relationship to IMP according to Investigator's opinion
- Number of episodes
- Onset of first occurrence CRS (at the first infusion and subsequent infusions)
- Day of onset from infusion (by category 1 day/ 2 to 3 days/ More than 3 days when applicable)
- Duration (in days) (by category 1 day/ 2 to 3 days/ More than 3 days)

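### The SAP ties no CRS, DLT or other adverse event to the infusion or dose that preceded it, although doses step up within each patient and the protocol planned part of this analysis

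*SAP*

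**What the plan says.** **Design.** Under Protocol 6.2.1, lead-in covers the first 2 doses in DL1 and DL2, "the first 3 doses in DL3 to DL5, and the first 4 doses in DL6 to DL8". A fixed dose follows, unless it has to be lowered for safety. Protocol 6.2.2 (study continuation) adds that "The Study Committee will also decide the RP2D, including the recommended lead-in dose and schedule".

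**SAP outputs.** SAP 4.1 sets the default strata: "analyses will be performed by part, by dose level (if applicable) and overall (if applicable". In SAP 4.7.2, DLTs and the other events of special interest are listed with preferred term and grade. CRS is examined further "with a listing providing a more detailed description of CRS by patient". Its items are action taken, relationship, number of episodes, day of onset from infusion, duration, and the one item that places the event in the treatment sequence: "Onset of first occurrence CRS (at the first infusion and subsequent infusions". On exposure, SAP 4.7.1.2 states: "A listing will be provided for cumulative dose, actual dose intensity and relative dose intensity". A separate listing flags dose reductions, omissions, interruptions and cycle delays by cycle and day.

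**Protocol analyses.** Protocol 13.4.4.2 also tabulates adverse events by dose level, but its CRS summaries include "Number (%) of patients with infusion of occurrence". For patients with Grade 3-4 laboratory abnormalities, Protocol 13.4.4.4 says that "additional analyses will be conducted to describe time to onset and dose to onset". It leaves similar exploration of other safety endpoints optional. SAP 5.2, the place for departures from protocol-planned analyses, is marked not applicable.

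**The concern.** Step-up dosing is used here to limit severe CRS (Protocol 6.2.1). To interpret the CRS data, one has to know where in the sequence each episode fell: on an early lead-in step, on the step just before the final dose, or on the final dose itself. A by-level table puts these together.

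The CRS listing helps only partly. It places the first episode and no later one, and it has two categories, the second of which covers several different doses. Day of onset from infusion gives the delay after an infusion but not which infusion it was. Cumulative dose and dose intensity describe the whole of treatment and cannot be turned back into a dose at onset.

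At stake is the reading of a primary safety endpoint. SAP 1.2 keeps the incidence of CRS and acute infusion reactions as a primary endpoint of the Dose Escalation Part, and SAP 4.3 keeps the primary safety analyses after the efficacy analyses were dropped. Two protocol-planned analyses that bear on this are also narrowed or missing, with no recorded reason.

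**Working it through.** The plan states no figure for this point, so there is none to reproduce. The check has three parts.

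**1. Does any specified output carry the dose or infusion before onset?**

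| Output | Places the event by | Infusion number? | Dose before onset? |
|---|---|---|---|
| AE tables (SAP 4.1, 4.7.2) | part, dose level | no | no |
| DLT and special-interest listings (SAP 4.7.2) | preferred term, grade | no | no |
| CRS listing (SAP 4.7.2) | first episode: first or subsequent infusion; days from infusion | no | no |
| Exposure listing (SAP 4.7.1.2) | patient totals | no | no |
| Dose-modification listing (SAP 4.7.1.2) | cycle/day, yes/no flags | no | no |

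None does, singly or combined.

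**2. How mixed is the category of later infusions in Cycle 1?** Let L be the number of lead-in infusions (Protocol 6.2.1) and T the Cycle 1 total: 6 in DL1-2 and 7 from DL3 up (Protocol 13.3.2). The lead-in share is L/T. The first infusion is always a lead-in dose, so the lead-in share of the later infusions is (L-1)/(T-1).

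| Levels | L | T | Target-dose infusions, T-L | L/T | (L-1)/(T-1) |
|---|---|---|---|---|---|
| DL1-2 | 2 | 6 | 4 | 2/6 = 33% | 1/5 = 20% |
| DL3-5 | 3 | 7 | 4 | 3/7 = 43% | 2/6 = 33% |
| DL6-8 | 4 | 7 | 3 | 4/7 = 57% | 3/6 = 50% |

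The remainder of 3 or 4 target-dose infusions agrees with Protocol 4.6, which expects at least 3 maximal doses in the DLT window.

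**3. What could this mean for first episodes?** As an illustration only, assume the same CRS probability q at every infusion, with q between 0.05 and 0.5. The documents give no such figure. Then, given a first CRS episode in Cycle 1:

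- P(it follows a lead-in dose) = [1-(1-q)^L] / [1-(1-q)^T]
- P(it follows a lead-in dose, given that it came after the first infusion) = [1-(1-q)^(L-1)] / [1-(1-q)^(T-1)]

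For DL6-8 at q = 0.05, the first is (1-0.95^4)/(1-0.95^7) = 0.1855/0.3017 = 61%. The second is (1-0.95^3)/(1-0.95^6) = 0.1426/0.2649 = 54%.

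| Levels | First episode at a lead-in dose, q 0.05 to 0.5 | Same, among first episodes after the first infusion |
|---|---|---|
| DL1-2 | 37% to 76% | 22% to 52% |
| DL3-5 | 47% to 88% | 37% to 76% |
| DL6-8 | 61% to 94% | 54% to 89% |

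Under this assumption, the category of subsequent infusions says little about whether the patient was at lead-in or at target dose.

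**The case against.** **Pooling by dose level is legitimate.** A reader might infer that lead-in events are wrongly credited to the target dose. The documents do not support that. A dose level is the whole Cycle 1 regimen and the unit of the 3+3 rule (Protocol 6.2.2), so counting a lead-in DLT under its level follows the design, and Protocol 13.4.4.2 tabulates by level too. This stands. The gap is that nothing finer is specified alongside.

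**The CRS item is narrow, and partly informative.** It would be wrong to read the first-versus-subsequent split as governing all adverse events. It concerns the first CRS episode in a by-patient listing, and it does isolate the first infusion, which is always lead-in. This stands, but later episodes and the remaining lead-in steps stay unplaced.

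**The RP2D does not hang on these outputs.** It is tempting to argue that the choice of RP2D, with its lead-in dose and schedule, is compromised. The SAP was written after early termination (SAP 4.3, 4.4 and 4.9), and the Study Committee judges escalation and the RP2D from data reviewed during the trial (Protocol 6.2.2 and 6.10). This stands.

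**The protocol asks for less than it may seem.** Infusion of occurrence is not dose, dose to onset is undefined and could mean cumulative dose, and wider dose-to-onset work was optional. All true. Still, one planned summary is reduced to two categories and another is absent, while SAP 5.2 reports no change.

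**The counts are design arithmetic.** They cover Cycle 1 only, the levels reached are not stated, and the doses are redacted. From Cycle 2 patients stay at their highest Cycle 1 dose, which lowers the lead-in share of all later infusions. This limits the size of the point but does not remove it.

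**Conclusion.** The point holds as a gap in the specified outputs and an unrecorded departure from the protocol. The SAP pools events under regimens in which 33%, 43% or 57% of Cycle 1 infusions are lead-in (DL1-2, DL3-5, DL6-8). For the first CRS episode it offers a later-infusion category in which 1 of 5, 2 of 6 or 3 of 6 Cycle 1 infusions are lead-in. No output gives the infusion number or the dose before onset.

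The consequence is limited interpretation of CRS incidence as a retained primary safety endpoint. It is not a wrong 3+3 count and not a flawed RP2D decision.

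The infusion counts assume dosing as scheduled. In practice CRS or other toxicity can hold escalation, cut the dose by a step or restart lead-in (Protocol 6.5), and gaps of 10 days or more also restart it (Protocol 6.2.2). Dose level and infusion number together would therefore still not give the dose. The need is sharpest for the first 3 patients, who may have been overdosed unintentionally and stay in the safety database (amendment summary of changes). The percentages in part 3 of the working rest on a constant per-infusion risk and must not be read as estimated misclassification rates.

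**What to change.** - In the CRS listing (every episode) and the DLT listing, add cycle and day, infusion number, planned and actual dose in ng/kg of the last infusion before onset, and a lead-in/target flag. Define the flag so that it also marks lead-in restarts after delay or toxicity.
- Restore the summary of patients with CRS by infusion of occurrence, and add a descriptive tabulation by dose received at onset.
- Restore dose to onset for Grade 3-4 laboratory abnormalities, stating whether it means the last dose or the cumulative dose, or record its omission with a reason in SAP 5.2.
- Flag the first 3 patients in these outputs, because their recorded and received doses may differ.

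**Cost.** A little more programming and no new data collection. The SAP already sums individual doses, compares each dose with the intended one, and counts days of CRS onset from infusion, so the inputs have to be in the database. No sample size, test or dosing rule changes. The by-dose tabulation remains descriptive: infusions within a patient are correlated, and later doses follow earlier step-up exposure, so rates at different dose steps are not independent comparisons.
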